8.1.3.3. Proportion of Subjects Achieving HbA_{1c} <7% at Week 26 and over Time

The proportion of subjects achieving HbA_{1c} target values of <7.0% at Week 26 and over time will be summarized by treatment and visit for the FA population. The treatment comparison will be carried out using the CMH test and logistic regression model described in Section 8.1.2.2. The proportion of subjects who responded over time will also be plotted using a bar chart.

If a subject has a missing HbA_{1c} value at week 26 and the reason why value is missing is not related to efficacy or safety (e.g., procedural) and could be assumed that value is missing at random, then the value will be left as missing for calculations; if the reason why value is missing is lack of efficacy or due to safety, then this missing value will be imputed as ‘not meeting target’ and included in the denominator in the calculation of the proportion of subjects achieving target HbA_{1c} <7%.

The results with the observed data and with imputed data will be both presented as part of sensitivity analysis.

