Secondary Analyses	
 • Categorical endpoints will be analyzed using CMH test and logistic regression adjusting for baseline HbA_{1c} category, age category, region and current use of metformin. Continuous endpoints will be analyzed using a MMRM model for the FA population. Time to event data will be analyzed using a log-rank test with Kaplan-Meier method.
Exploratory Analyses	
 • Exploratory endpoints will be analysed in a similar manner as described above for the secondary endpoints.
Safety Analyses	
 • Adverse events, adverse events of special interest, hypoglycemic events, clinical laboratory tests, vital signs and ECG findings will be presented by treatment groups.

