8.1.2. Key Secondary Efficacy Endpoints

8.1.2.1. Proportion of Subjects Who Do Not Meet Prespecified Criteria for Severe, Persistent Hyperglycemia through Week 26

For this key secondary endpoint, subjects who do not meet prespecified criteria for severe, persistent hyperglycemia through Week 26 will be defined operationally as those subjects treated with once-weekly albiglutide that are able to replace prandial insulin without lispro re-introduction through Week 26. Note: For lispro re-introduction through Week 26 the time window is defined up to Week 25.

Proportion of subjects that are able to discontinue insulin lispro at Week 4 and do not meet prespecified criteria for severe, persistent hyperglycemia through Week 26 will be summarized descriptively for all the Albiglutide + Insulin Glargine arm subjects and for

subgroups of baseline HbA_{1c} category (<8.0%, ≥8.0%), region, (<65 years versus ≥65 years), current use of metformin (Yes, No) in the FA population. The 95% confidence interval of the proportions of subjects will be provided.

The insulin lispro that was re-introduced to albiglutide subjects will be characterized. Summary statistics for the number of injections, total dose, and time-to-re-introduction will be presented.

Additional exploratory analyses to identify potential risk factors for lispro re-introduction will be investigated. Potential risk factors include: baseline HbA_{1c}, baseline HbA_{1c} category, age, age category, metformin-use, duration of diabetes, weight, BMI, BMI category, time in insulin (at baseline), baseline HbA_{1c}, and total insulin dose at baseline. Time in insulin (at baseline) is defined as the earliest start date of prior insulin medications taken minus the date of first date of randomized study medication, plus 1.

8.1.2.2. Percentages of Subjects with Severe or Documented Symptomatic Hypoglycemia through Week 26

The percentage of subjects with severe or documented symptomatic hypoglycemia will be summarized descriptively by treatment and analyzed using a Cochran-Mantel-Haenszel (CMH) test, stratified by baseline HbA_{1c} category, region, age category (<65 years versus ≥65 years), current use of metformin (Yes, No) in the FA population.

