As supportive analysis, logistic regression models adjusting for baseline HbA_{1c} category, region, age category and current use of metformin will be used to quantify the treatment effects. Odds ratio for treatment and the associated confidence interval will be used to estimate the treatment difference.

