8.1.3.4. Proportion of Subjects Achieving HbA_{1c} <6.5% at Week 26 and over Time

Proportion of subjects achieving HbA_{1c} target values of <6.5% at Week 26 and over time will be analyzed and summarized in a similar manner as specified in Section 8.1.3.3.

8.1.3.5. Incidence and Time to Meeting Prespecified Criteria for Severe, Persistent Hyperglycemia through Week 26

In this treat-to-target study design, subjects may be withdrawn if they have severe and persistent hyperglycemia. Meeting prespecified criteria for severe, persistent hyperglycemia at week 26 will be defined operationally as being withdrawn due to lack of efficacy as recorded on the Treatment Discontinuation and Study Conclusion eCRF pages. Proportion of subjects who meet prespecified criteria for severe, persistent hyperglycemia at Week 26 will be summarized and analyzed in a same manner as described in Section 8.1.2.2.

The time to meeting prespecified criteria for severe, persistent hyperglycemia through Week 26 will be calculated as the number of days between the date of first dose of randomized study medication and the date of meeting prespecified criteria, persistent hyperglycemia, plus 1. Subjects who do not meet the criteria will be censored at the date of the Week 26 visit or the date of the early termination visit if the subject terminated the study early. Kaplan-Meier estimates of the median time to meeting the criteria and 95% confidence interval for each treatment group will be presented. The treatment difference will be assessed using a log-rank test. The proportion of subjects meeting the criteria up to Week 26 (Day 182) based on Kaplan-Meier estimates will be displayed in the summary table. Kaplan-Meier curves of the times to meeting the criteria for each treatment group will be presented.

The analysis will be performed on FA population and all data will be listed.

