8.1.3.6. Composite Endpoints

The following composite endpoints (after 26 weeks of treatment) will be analyzed as secondary efficacy endpoints:

- Percentage of subjects achieving $\text{HbA}_{1c} < 7.0\%$ without weight gain
- Percentage of subjects achieving $\text{HbA}_{1c} < 7.0\%$ without severe or documented symptomatic hypoglycemia
- Percentage of subjects achieving $\text{HbA}_{1c} < 7.0\%$ without weight gain and without severe or documented symptomatic hypoglycemia

No weight gain is defined as ≤ 1 kg increase from baseline in body weight. These composite endpoints will be analyzed and summarized in a similar manner as specified in Section 8.1.2.2.

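### The HbA1c target endpoints adjust for baseline HbA1c only as below or above 8.0%; entering the continuous value in the logistic model would recover a little precision at almost no cost

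*SAP*

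**What the plan says.** SAP 8.1.3.3 covers HbA1c <7.0%: "The treatment comparison will be carried out using the CMH test and logistic regression model described in Section 8.1.2.2". SAP 8.1.3.4 says that HbA1c <6.5% "will be analyzed and summarized in a similar manner as specified in Section 8.1.3.3". SAP 8.1.3.6, on the three secondary composites that include HbA1c <7.0%, says: "These composite endpoints will be analyzed and summarized in a similar manner as specified in Section 8.1.2.2". SAP 8.2.8 sends its exploratory HbA1c composite to 8.1.2.2 as well.

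SAP 8.1.2.2 is the hypoglycemia section. Its main test is a CMH test "stratified by baseline HbA_{1c} category, region, age category" and metformin use. Its supportive analysis uses "logistic regression models adjusting for baseline HbA_{1c} category, region, age category and current use of metformin", and the treatment odds ratio and its interval come from that model. The cut-point is given in 8.1.2.1, which lists "subgroups of baseline HbA_{1c} category (<8.0%, ≥8.0%), region" among the subgroups. The SAP synopsis agrees: "Categorical endpoints will be analyzed using CMH test and logistic regression adjusting for baseline HbA_{1c} category".

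Protocol 8.3.3.2 takes the same approach. It handles the other binary secondary endpoints like the hypoglycemia proportion, with the HbA1c stratum as the HbA1c term.

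The primary MMRM (SAP 7.1.1.1, Model 1) instead uses continuous baseline HbA1c, with a by-week interaction, next to region, age category and metformin.

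**The concern.** HbA1c <7.0% at Week 26 is the primary measurement cut at a threshold, yet it is analysed without the continuous baseline that the primary model uses. Protocol 4.4 limits randomization to 7.0% to 9.0% at Week -1, so one cut at 8.0% splits the range into two wide halves. A subject at 7.1% and one at 7.9% are modelled as having the same chance of finishing below 7.0%. If baseline HbA1c is prognostic, they do not.

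For continuous endpoints, Protocol 8.3.3.2 justifies adjusting for the endpoint's own baseline as a way to reduce variance and to allow for chance imbalance. The same reasoning applies to these binary endpoints. What is at stake is some precision in the adjusted treatment odds ratio for supportive and exploratory endpoints.

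**Working it through.** **1. The plan's own figure.** The SAP sizes only the primary noninferiority test (Appendix 12: margin 0.3%, SD 1.2%, one-sided 0.025, 90% power).
- n per arm = 2 × (1.960 + 1.282)² × 1.2² / 0.3² = 336.2, rounded up to 337.
- 337 / 0.85 = 396.5, so 397 per arm and 794 in total.

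Both figures reproduce and neither is affected by this point. No power is stated for the target endpoints.

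**2. Which analysis can change.** The CMH test crosses 2 HbA1c categories, 6 regions (SAP Appendix 8), 2 age categories and 2 metformin categories: 2 × 6 × 2 × 2 = 48 strata. That is about 674 / 48 = 14 completers per stratum. CMH cannot take a continuous covariate, so only the logistic model is at issue.

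**3. What the 8.0% split already captures.** Assume baseline HbA1c is normal with mean 8.0 and SD 0.6, truncated to 7.0–9.0%. Its SD is then 0.478, and the SD within a category is 0.265. The split captures 1 − 0.265² / 0.478² = 69% of the baseline variance, so the remaining gain has to be small.

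**4. Logistic model, category versus continuous baseline (simulation).** Assumed model:
- Week 26 HbA1c = 7.2 + slope × (baseline − 8.0) − 0.2 × (albiglutide) + normal error.
- 337 per arm, two-sided 5% Wald test, 2,000 to 3,000 replicates per row.
- Region, age and metformin are left out of both models.
- SD of change = √[(1 − slope)² × 0.478² + residual SD²].

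Only the 337 per arm and the SD of 1.2% come from the plan.

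| SD of change | Slope | Residual SD | Target | Power, category | Power, continuous | Gain (points) |
|---|---|---|---|---|---|---|
| 1.20 | 0.6 | 1.18 | <7.0% | 40.7% | 40.7% | 0.0 |
| 1.20 | 0.8 | 1.20 | <7.0% | 39.5% | 39.9% | 0.4 |
| 1.20 | 0.6 | 1.18 | <6.5% | 37.5% | 37.9% | 0.4 |
| 1.20 | 0.8 | 1.20 | <6.5% | 35.0% | 35.7% | 0.7 |
| 0.96 | 0.3 | 0.9 | <7.0% | 62.6% | 62.6% | 0.0 |
| 0.83 | 0.5 | 0.8 | <7.0% | 71.4% | 71.8% | 0.4 |
| 0.71 | 0.7 | 0.7 | <7.0% | 80.0% | 81.2% | 1.2 |
| 0.70 | 0.9 | 0.7 | <7.0% | 77.2% | 78.8% | 1.6 |
| 0.70 | 0.9 | 0.7 | <6.5% | 66.6% | 69.0% | 2.4 |
| 0.61 | 0.8 | 0.6 | <7.0% | 86.6% | 88.7% | 2.1 |

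Effective sample size is compared as the ratio of squared mean Wald z. At SD 1.2% the gain is about 1 to 2%. Over the smaller SDs it is about 0.5 to 7.5%, or 0 to 3 power points. The continuous term lost power in no scenario.

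**5. Validity.** With no true difference, rejection rates at the smaller SDs were 4.1% to 5.8% across the two models. The Monte Carlo standard error is √(0.05 × 0.95 / 2000) = 0.5 points. Neither model has a type I error problem.

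**6. Chance imbalance within category.** The standard error of the arm difference in mean baseline, within category, is 0.265 × √(2/337) = 0.02% HbA1c, which is negligible. Where the odds ratio moves (1.57 to 1.60 at slope 0.7, target <7.0%), the shift is what a more strongly conditioned odds ratio shows through non-collapsibility.

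**The case against.** The strongest reply is that nothing here is wrong. Protocol 8.3.3.2, the SAP synopsis and SAP 8.1.2.2 agree, and adjusting for categorical baseline factors is conventional and valid. The target endpoints stand outside the testing hierarchy in SAP Appendix 10, and tests on them are exploratory. The CMH test does not move. Continuous baseline is already used where HbA1c inference counts, in the primary MMRM. At the plan's own SD the gain is below one power point. Even that supposes a true difference of 0.2%, whereas the plan assumes 0.0% and Appendix 10 expects no significant HbA1c difference in a treat-to-target design.

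All of this stands, and it sets the grade. It does not show that the category is preferable. The logistic model is where the treatment effect is estimated, and a more efficient covariate is available in data already collected.

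A reader might infer that the model was carried over by oversight, or that the cut at 8.0% leaves the odds ratio biased. The documents support neither. The protocol prescribes the approach, randomization protects the comparison, and the shift in the odds ratio fits non-collapsibility. Nor do the documents say that baseline HbA1c strongly predicts reaching target. That is plausible, since Week 26 HbA1c is baseline plus change, but it remains an assumption.

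The change has two small costs of its own. It assumes that the logit is linear in baseline HbA1c, and it leaves the CMH and logistic analyses adjusting for different forms of baseline.

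**Conclusion.** The point holds as a minor gain in efficiency. The planned logistic model for HbA1c <7.0%, <6.5% and the HbA1c composites is valid and matches the protocol. It leaves a small amount of precision unused by reducing baseline HbA1c to two levels.

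The size is about 1 to 2% effective sample size at the plan's SD of change of 1.2%, and about 0 to 3 power points if the SD is smaller. Figures near the top of that range need both a small SD and a steep dependence on baseline, and should not be quoted alone.

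The estimate rests on the assumed baseline distribution, slopes and 0.2% difference. It was obtained for the two HbA1c thresholds at Week 26. For the composites, where weight gain or hypoglycemia also decides the outcome, the gain was not examined. The primary analysis, the sample size and the testing hierarchy are untouched.

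**What to change.** In SAP 8.1.3.3, 8.1.3.4, 8.1.3.6 and 8.2.8, state that the logistic model uses continuous baseline HbA1c in place of the two-level category, with region, age category and metformin kept. These are the baseline covariates of Model 1. Leave the CMH test as the stratified analysis, and leave the hypoglycemia model in 8.1.2.2 as it is. Enter the change in the SAP 2.1 table of departures from the protocol, before the database is frozen.

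The cost is one covariate in a few supportive models and one line in SAP 2.1, with no new data. A standardized risk difference from the same model would be easier to read than an odds ratio, but it is optional and not part of this change.

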8.1.3.4. Proportion of Subjects Achieving HbA_{1c} <6.5% at Week 26 and over Time

Proportion of subjects achieving HbA_{1c} target values of <6.5% at Week 26 and over time will be analyzed and summarized in a similar manner as specified in Section 8.1.3.3.

8.1.3.5. Incidence and Time to Meeting Prespecified Criteria for Severe, Persistent Hyperglycemia through Week 26

In this treat-to-target study design, subjects may be withdrawn if they have severe and persistent hyperglycemia. Meeting prespecified criteria for severe, persistent hyperglycemia at week 26 will be defined operationally as being withdrawn due to lack of efficacy as recorded on the Treatment Discontinuation and Study Conclusion eCRF pages. Proportion of subjects who meet prespecified criteria for severe, persistent hyperglycemia at Week 26 will be summarized and analyzed in a same manner as described in Section 8.1.2.2.

The time to meeting prespecified criteria for severe, persistent hyperglycemia through Week 26 will be calculated as the number of days between the date of first dose of randomized study medication and the date of meeting prespecified criteria, persistent hyperglycemia, plus 1. Subjects who do not meet the criteria will be censored at the date of the Week 26 visit or the date of the early termination visit if the subject terminated the study early. Kaplan-Meier estimates of the median time to meeting the criteria and 95% confidence interval for each treatment group will be presented. The treatment difference will be assessed using a log-rank test. The proportion of subjects meeting the criteria up to Week 26 (Day 182) based on Kaplan-Meier estimates will be displayed in the summary table. Kaplan-Meier curves of the times to meeting the criteria for each treatment group will be presented.

The analysis will be performed on FA population and all data will be listed.

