8.3.3.2. Other Comparisons of Interest

A key secondary endpoint is the proportion of subjects treated with once-weekly albiglutide that are able to replace prandial insulin without the need for re-introduction of insulin lispro. The 95% confidence interval of the sample proportion will be estimated, stratified by region, age category, and current use of metformin.

The proportion of subjects with hypoglycemia, as confirmed by plasma glucose monitoring <70 mg/dL (<3.9 mmol/L) and/or requiring third-party intervention through Week 26, will be compared between treatment groups, adjusting for baseline HbA_{1c} stratum, age group, current use of metformin, and region.

Other binary secondary endpoints, such as the proportion of subjects achieving HbA_{1c} treatment goals at Week 26 and the proportion of subjects achieving composite secondary endpoints (i.e., criteria involving HbA_{1c} target and hypoglycemia) will be analyzed analogous to the proportion of subjects with hypoglycemia.

Continuous secondary endpoints, e.g., changes over time in HbA_{1c}, FPG, and body weight, changes in daily insulin dose, changes in mean daily blood glucose based on 8-point SMBG, and changes in total number of weekly insulin injections will be summarized descriptively and analyzed using an MMRM (observed data). In the MMRM for non-HbA_{1c} endpoints, the corresponding baseline variable will be modeled as a covariate (in place of baseline HbA_{1c}) for variance reduction and to adjust for any baseline differences in treatment groups attributable to chance as well as the randomization stratification variables (HbA_{1c} stratum, age category, current use of metformin).

The number of hypoglycemic events with confirmed home blood glucose monitoring <70 mg/dL (<3.9 mmol/L) and/or requiring third-party intervention in 3-month intervals (i.e., from Baseline/Randomization to Week 12, >Week 12 to Week 26) will be compared between the treatment groups using a Poisson regression model with offset for the person-year, which will include treatment effect and covariates such as HbA_{1c} stratum, age (<65 years versus ≥65 years), current use of metformin (metformin use versus no metformin use), and region.

The time to meeting prespecified criteria for severe, persistent hyperglycemia at Week 26 will be analyzed for treatment group differences using pairwise log-rank tests within a Kaplan-Meier model.

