8.1.2.3. Change from Baseline in Body Weight at Week 26 and over Time

Change from Baseline in body weight will be analyzed and summarized analogous to the primary efficacy endpoint using a slightly different MMRM model which includes change from Baseline in body weight as dependent variable; treatment, region, baseline HbA_{1c} category, age category, current metformin use, visit week, treatment-by-week interaction, and baseline weight-by-week interaction as fixed effects; baseline weight as a continuous covariate; and subject as a random effect (Model 2). Treatment difference at Week 26 will be tested; p-value and 2-sided 95% confidence interval will be presented. The percentage change from baseline in body weight will be analysed using a similar MMRM model:

Change from Baseline in Body Weight = Baseline Body Weight + Treatment + Baseline HbA_{1c} Category + Region + Age Category + Current Use of Metformin + Visit Week + Treatment-by-Visit Interaction + Baseline Body Weight-by-Visit Week Interaction (Model 2).

The percentage change from Baseline in body weight will be analyzed similarly using Model 2 above, with percent change from baseline in body weight as the dependent variable.

The observed body weight values and change and percent change from baseline body weight will be summarized descriptively and presented graphically. The least squares means (and standard errors) of change from baseline body weight will be plotted by treatment group.

The analyses will be performed on FA population and all data will be listed.

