11.6.3.2. Reasons for Withdrawal

Reasons for withdrawal are assumed to fall into three broad categories:

- Procedural (i.e. lost to follow-up, investigator site closed, withdrew consent, protocol deviation, and investigator discretion that are not related to study treatment): In this case, it is expected that an assumption of missing at random (MAR) is appropriate for imputation of HbA_{1c} data after withdrawal.
- Safety (i.e. AE; subject reached protocol-defined stopping criteria; withdrew consent, protocol deviation, and investigator discretion that are related to study treatment): It is expected that, in most cases, any change in safety related to these reasons for withdrawal would have been captured prior to the subject withdrawing from the study. In Study GLP108486 (albiglutide versus lispro over background glargine), 5% of subjects in the albiglutide group and <1% in the lispro group had AEs leading to withdrawal of active treatment through Week 26. In the albiglutide group, the most common AE leading to withdrawal was injection site reaction (1.1%). Missing HbA_{1c} values after withdrawal due to safety concerns will be considered to possibly be missing not at random (MNAR).

- Lack of efficacy: In this treat-to-target study, a substantial number of cases of withdrawal due to lack of efficacy is not expected. Missing HbA_{1c} values after withdrawal due to lack of efficacy are considered to possibly be MNAR.

Sensitivity analyses will be performed for data missing due to safety concerns or due to lack of efficacy.

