11.9. Appendix 9: Examination of Covariates, Subgroups & Other Strata

11.9.1. Strata and Covariates

The randomization for this study is stratified by the following baseline characteristics:

- HbA_{1c} at Screening (<8.0% versus $\geq 8.0\%$)
- Age at randomization (<65 years versus ≥ 65 years)
- Current use of metformin (metformin use versus no metformin use)

The primary analysis of HbA_{1c} change from Baseline will use a mixed-effect model with repeated measures (MMRM), which includes HbA_{1c} change from Baseline at all postbaseline visits as dependent variables; treatment, region, age category, current use of metformin, visit week, treatment-by-week interaction, and baseline HbA_{1c}-by-week interaction as fixed effects; baseline HbA_{1c} as a continuous covariate; and subject as a random effect. MMRM will only include non-missing observations therefore imputation will not be performed.

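### The log-rank test for time to severe, persistent hyperglycemia leaves out the three randomisation strata: valid, but marginally conservative and slightly less efficient if those strata are prognostic

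*SAP*

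**What the plan says.** Three places describe the test, and they agree:

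- SAP Section 8.1.3.5: "The treatment difference will be assessed using a log-rank test".
- SAP synopsis: "Time to event data will be analyzed using a log-rank test with Kaplan-Meier method".
- Protocol Section 8.3.3.2: the time to meeting the criteria "will be analyzed for treatment group differences using pairwise log-rank tests within a Kaplan-Meier model".

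None names a stratum or covariate.

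SAP Section 11.9.1 opens with "The randomization for this study is stratified by the following baseline characteristics" and lists screening HbA1c (<8.0%, ≥8.0%), age (<65, ≥65 years) and metformin use. That makes 2 × 2 × 2 = 8 cells.

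The other between-group secondary analyses do adjust. In the synopsis, categorical endpoints are tested by CMH and logistic regression "adjusting for baseline HbA_{1c} category, age category, region and current use of metformin". The body-weight model in SAP Section 8.1.2.3 contains "treatment, region, baseline HbA_{1c} category, age category, current metformin use, visit week, treatment-by-week interaction", and the other continuous secondary endpoints outside HbA1c follow it.

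The event itself is "defined operationally as being withdrawn due to lack of efficacy" (SAP Section 8.1.3.5), and SAP Section 11.6.3.2 says that "a substantial number of cases of withdrawal due to lack of efficacy is not expected".

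**The concern.** When randomisation is balanced within strata and the strata predict the outcome, the between-stratum part of the outcome variation cannot differ between arms. An unstratified test still counts that part in its variance. Its p-values are then a little too large and it gives up some power. It is plausible, though the documents do not quantify it, that screening HbA1c predicts withdrawal for lack of efficacy.

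The contrast is sharpest inside SAP Section 8.1.3.5. Its first paragraph sends the incidence of this event to the method of Section 8.1.2.2, a CMH test stratified by baseline HbA1c category, region, age category and metformin use. The next paragraph tests the time to the same event with no strata. The report would carry two p-values on one set of events under different adjustment rules, with no reason given. What is at stake is a little efficiency and some consistency on one supportive endpoint.

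**Working it through.** **The plan's own figure.** The documents give no event count, effect size or power for this log-rank test. Their one sample size is for HbA1c non-inferiority, and it reproduces: 2 × 1.2² × (1.960 + 1.282)² / 0.3² = 336.3, so 337 per group; 337 / 0.85 = 396.5, so 397 per group and 794 in all. Power at 337 is 90.06%. Stratifying the log-rank test does not touch this.

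**Inputs from the documents.** 794 subjects randomised 1:1, eight strata, 15% dropout. The two-sided 0.05 level is stated for the testing hierarchy and is used here as the nominal level.

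**Inputs assumed.** Cell prevalences (HbA1c ≥8.0% 50%, age ≥65 30%, metformin 60%), event risks, stratum hazard ratios (written HbA1c/age/metformin), treatment hazard ratios, and blocks of 4.

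**Analytic size.** With cell risks p_s and overall risk p, the variance ratio is r = 1 − Var(p_s) / [p(1 − p)], and the size of the unstratified test is 2[1 − Φ(1.96/√r)].

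Worked example: p = 5%, hazard ratios 3/1.5/1.5. For rare events p_s is proportional to the product of the hazard ratios, so its squared coefficient of variation is a product over factors of E(m²)/E(m)², minus 1:

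- HbA1c: (0.5 + 0.5 × 9) / 2² = 1.25
- Age: (0.7 + 0.3 × 2.25) / 1.15² = 1.040
- Metformin: (0.4 + 0.6 × 2.25) / 1.3² = 1.036

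The product is about 1.346, so r ≈ 1 − 0.05 × 0.346 / 0.95 = 0.982. Without the rare-event shortcut r = 0.9828, and the size is 0.0480.

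| Event risk | 1.5/1/1 | 2/1.25/1.25 | 3/1.5/1.5 | 5/2/2 |
|---|---|---|---|---|
| 2% | 0.0499 | 0.0497 | 0.0492 | 0.0482 |
| 5% | 0.0498 | 0.0492 | 0.0480 | 0.0457 |
| 10% | 0.0495 | 0.0484 | 0.0461 | 0.0416 |
| 30% | 0.0486 | 0.0454 | 0.0388 | 0.0281 |

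**Simulated size** (8,000 trials per setting), unstratified versus stratified by the 8 cells:

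- 2% risk: 4.46% vs 4.59% (2/1.25/1.25); 4.2% vs 4.3% (2/1.4/1.4); 4.6% vs 4.8% (4/2/2)
- 5% risk: 4.74% vs 4.84% (2/1.25/1.25); 4.84% vs 4.99% (3/1.5/1.5); 4.8% vs 4.9% (2/1.4/1.4); 4.2% vs 4.7% (4/2/2)
- 10% risk: 4.7% vs 4.8% (2/1.4/1.4); 4.1% vs 4.7% (4/2/2)

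The Monte Carlo standard error of one size is √(0.05 × 0.95 / 8000) = 0.24 points, so the analytic result carries the direction. At 2% risk (about 15 events in the first setting) both tests run below 5%. That part is sparsity, which stratifying does not cure.

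**Simulated power** (6,000 trials per setting):

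| Control risk | Treatment HR | Strata HRs | Unstratified | Stratified |
|---|---|---|---|---|
| 2% | 3 | 2/1.25/1.25 | 78.2% | 78.3% |
| 5% | 2 | 2/1.25/1.25 | 68.5% | 68.7% |
| 5% | 2 | 3/1.5/1.5 | 68.5% | 69.2% |
| 10% | 1.7 | 3/1.5/1.5 | 71.0% | 72.6% |

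With hazard ratios 2/1.4/1.4 and 4/2/2 and treatment HR 2, the gain was about 0.4 to 1.8 points at 2% to 5% risk and −0.1 to 1.6 points at 10%. A further run (4,000 trials per setting, six settings) gave sizes of 4.2% to 5.4% unstratified and 4.5% to 5.5% stratified, and power changes of −0.2 to +1.6 points. Mean z was higher with stratification in all six.

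**Scale.** By Schoenfeld's formula, power is Φ(√d × ln(HR)/2 − 1.96). At HR 2, 16 events (2% of 794) give 28.3% and 40 events give 59.2%. The event count matters far more than stratification.

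**The case against.** The strongest reply is that this is a preference rather than an error. The unstratified test is valid after stratified randomisation, any departure is on the safe side, and protocol and SAP agree with each other. An adjusted comparison of the same event already exists through the CMH test and logistic regression on incidence. The endpoint sits outside the hierarchy in SAP Section 11.10 and gets only a nominal p-value. Few events are expected, which is where the effect is smallest. All of this stands, and it caps the point at a minor improvement. It does not give a reason for leaving the strata out.

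It is also fair that a test stratified by the randomisation factors would still not match the CMH test, which uses baseline rather than screening HbA1c and adds region. Full matching is not worth pursuing: 8 cells × 6 regions = 48 cells would be too sparse.

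A reader might infer that the test is seriously conservative, with a size well under 4%. In the analytic grid that needs events to be common (0.0388 and 0.0281 at 30% risk with strong strata), and the SAP expects the opposite. A reader might also infer that the event has no adjusted analysis. SAP Section 8.1.3.5 shows that it has one.

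**Conclusion.** The point holds as a small, optional improvement. The log-rank test is specified without strata although randomisation was stratified and the companion incidence test is stratified. If the strata are prognostic, the test is marginally conservative: its size is about 4% to 5% for event risks of 2% to 10% and stratum hazard ratios up to 4/2/2. Stratifying changes power by roughly 0 to 2 points. If the strata are not prognostic, nothing is lost. Every magnitude rests on assumed event risks, prevalences and hazard ratios, because the documents supply none. The primary result, the key secondary tests and the sample size of 794 are unaffected.

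**What to change.** - In SAP Section 8.1.3.5, name a log-rank test stratified by the three randomisation factors, using the values recorded in the IVRS: screening HbA1c, age group and metformin use.
- Do not add the six regions.
- State that cells with no events contribute nothing to the test, and show the unstratified test as a sensitivity analysis.
- Amend the time-to-event sentence in the SAP synopsis, and add a row to the table of changes in SAP Section 2.1, since Protocol Section 8.3.3.2 names the plain test.
- Leave the Kaplan-Meier estimates and curves as planned.

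The cost is a few lines of SAP text and one SAS statement. The factors are already collected for randomisation, and no new data or subjects are needed.
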